#### **E. Definition of Primary and Secondary Outcomes / Endpoints:**

##### **Primary Outcome Measures**

The overall goal of this study is to examine the change in PTH and / or axial neck pain in groups of patients receiving minimally invasive nerve block interventions (ONB with lidocaine and steroids vs. CMBB with lidocaine and steroids). The primary outcome is defined as change in pain

intensity scores (NRS), which will be collected at baseline, weekly for two months, and then bi-weekly throughout rest of the study.

Pain scales: The numerical rating scale (NRS) will be utilized in this study. Patients will rate their pain score on a scale of 0 to 10 with 0 being no pain and 10 being the worst pain imaginable.

### **Secondary Outcome Measure**

The secondary outcome measures include data about associated pain and psychological comorbidities, and concomitant effects of intervention.

- Headache frequency and severity: The MIDAS and PedMIDAS are brief questionnaires, which are self-administered to quantify headache-related disability. The MIDAS score has been shown to have moderately high test-retest reliability in headache sufferers and is correlated with clinical judgment regarding the need for medical care.
- Functional Disability: The Functional Disability Inventory (FDI) is a valid and reliable measure consisting of 15 items concerning perceptions of physical and psychosocial functioning. Total scores range from 0 to 60 with higher scores indicating greater disability. The Pain Disability Index (PDI) is a simple and rapid instrument used to measure the impact that pain has on the ability of a person to participate in essential life activities. Participants will rate their disability using a scale of 0 to 10 where 0 indicates no disability and 10, total disability.
- QL Scores: QL (Quality of Life Questionnaire) and PedsQL is a brief, standardized, generic assessment instrument that systematically assesses adult patients and pediatric patients / parent's perceptions of health-related quality of life (HRQOL) with chronic health conditions. The QL is based on a modular approach to measuring HRQOL and consists of a 15-item core measure of global HRQOL that includes physical, emotional, school and social domains of function
- Time to return to sports, school and/or work in weeks

### **Other Independent Variables**

- Socio-demographic characteristics: Age and BMI, which will be reported as a continuous variable and sex, will be reported as a dichotomous variable.
- Physical exam characteristics will be described as a categorical variable and classified as: Headaches (migrainous, cervicogenic/tension type, neuralgic or mixed) and / or axial neck pain (with extension, flexion, or extension and flexion)

- Presence of headaches, neck pain, or whole body pain before the intervention, which will be reported as a continuous variable in number of months. Concussion symptom scores will be collected using the Concussion Symptom Inventory, a symptom scale designed for tracking recovery/improvement from concussion headache.
- Presence of psychological comorbidities such as anxiety and depression will be assessed over the course of the study using the Patient-Reported Outcomes Measurement Information System (PROMIS) Anxiety Symptoms Scale and the PROMIS Depressive Symptoms Scale. Both scales have demonstrated reliability and validity, including internal consistency and convergent/divergent validity.
- Presence of pain related comorbidities such as whole body pain, gastrointestinal problems, fibromyalgia and small fiber neuropathy will be classified as a categorical variable.
- Presumed anatomic diagnosis will be described as a categorical variable and classified as: Facet arthropathy, occipital neuralgia, myofascial spasms, spondyloysis, spondylolisthesis, axial, discogenic pain.

#### **F. Data Collection Methods**

All patients will be assigned a unique personal identifier that will not be linked to any patient identifying information. Data will be collected during the study in case report forms and then will be entered into an Excel database, data from the email follow ups will be collected in REDCap and extracted and merged into the master Excel database.

Research information collected during the study will be stored in locked cabinets with access limited to the Principal Investigator and research personnel affiliated with the study. All health information is protected by HIPAA (Health Insurance Portability and Accountability Act) and all health records will be kept confidential. Patients' birthdate, name, and all other identifying information will be removed when analyzing and reporting on the data. Any personal identifying information will be stored separately from the other information the patient gives us and no personal identifying information will be reported in any publications or presentations. Identifying information will be kept in a password protected, secure file with limited access by research personnel. Once data collection is complete, identifying information will be destroyed.

#### **G. Data Management Methods**

All relevant information retrieved from the electronic medical record, by the PI and/or a member of staff will be translated into an electronic form. Data collected in paper case report forms will be entered into a 21 CFR Part 11 compliant database, InForm Electronic Data Capture (EDC) Systems, for intake and checking, and will be protected by encryption and password. We will administer a baseline survey, followed by weekly or bi-weekly REDCap questionnaires that include information regarding post-procedure pain intensity scores, functional disability scores, anxiety and depression scores, and symptoms scores using REDCap questionnaires. The data obtained from these REDCap surveys will be maintained in the study's REDCap database. REDCap is a secure, web-based application designed to support electronic data capture for research. Only authorized users are permitted access to the data files, and daily server back-up activities are executed to ensure data recovery. All data will be stored on a password-secured research computer, and all data entered into the computers will be password protected. Procedures to ensure accurate and reliable data collection will include well designed data forms and training.

## **H. Quality Control Methods**

Data quality control will be assured through automated and manual methods. The study database enhances data quality through required entry fields for critical data and automatic flags for missing or out-of-range data. Efforts will be made to minimize data entry error by the development of a user-friendly database and all data entry will be double-checked with the source files.

## **I. Data Analysis Plan and Sample Size**

At the time of data analysis, datasets will be downloaded from both REDCap and InForm and merged into Statistical Analysis Systems 9.3 for purposes of analysis. Missing data will be accounted for when the data is coded into respective variables.

In order to detect a 30% difference between treatment groups, and with an  $\alpha$  of 0.05 and  $\beta$  of 0.8, we will need a sample size of 24 subjects per group. Taking into consideration a 30% dropout rate during the study, we estimate a sample size of 63 subjects in the trial.

We will analyze pain scores (NRS), MIDAS/ PedMIDAS, FDI and QL scores as continuous variables. Differences of these parameters from baseline will be the outcomes variables. The differences in pain, functional, and QL scores will first be tested for normality. Assuming normality, T-Tests will be conducted to investigate the differences between the two randomized

groups. If data does not appear to be normal, Wilcoxon Rank Sum Tests will be performed in contrast to T-Tests.

Descriptive statistics will be generated in order to summarize socio-demographic characteristics of study participants. Frequency tables will be generated to describe gender, psychological and pain related comorbidities, history of injury, previous treatment methods and interventions. Similarly, frequency tables will be generated to depict physical exam characteristics, presumed anatomic diagnosis provided by clinicians, and presence of any predictive clinical findings. Continuous characteristics such as age and BMI will be tested for normality using the Shapiro-Wilk test. Continuous characteristics will be summarized using mean and standard deviation if the distribution appears normal, or will be summarized using median and interquartile range if the distribution does not appear normal. We will evaluate baseline differences between responders and non-responders, using chi-square and t-test for categorical and continuous variables, respectively.

Additionally, pain, functional, and QL scores will be assessed at multiple time points after treatment. Repeated measure analysis will be used to compare the pain, functional and QL scores over time between groups and compared with baseline values. We will also use multiple regression analysis where treatment, epidemiological, clinical, and psychosocial characteristics will be used as independent variables. Exploratory analysis comparing the two interventional groups will also be performed in order to generate future hypothesis of the best sequential treatment algorithm in PTH.

The fluoroscopy time and radiation exposure amount will be checked for normality using the Shapiro-Wilk Test. If data is assumed to be normal, an analysis of variance will be conducted to assess difference in mean fluoroscopy time and radiation exposure amount. If data does not appear normal, a Kruskal-Wallis test will be performed.

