**3. Description of Study Treatments or Exposures/Predictors**

Patients enrolled in the study will be randomized to receive either an ONB (Figure 2, additional procedure details provided below) with dexamethasone 2mg each site with 3ml 1% lidocaine, for a total of two sites or a CMBB (Figure 3a & 3b, additional procedure details provided below) with dexamethasone 1.5mg each site with 2 ml 1% lidocaine, for a total of three sites on each side. The assignment of the procedure will be randomized however neither the patients nor the investigator will be blinded to the procedure. If patients exhibit a  $\geq 50\%$  pain reduction on receiving the block evaluated after four weeks, then they may continue to receive blocks as needed, but not more than one every three months. If patients exhibit  $< 50\%$  pain reduction, the patient will be treated as per the clinician's judgment with the possibility of a cross over to the other treatment option in the protocol.

All patients will be followed for 12 months after enrollment and after the crossover of treatments they will continue to be treated and followed per clinical standard of care.

As part of this study, patients will need to complete 8 follow-up visits, of which the first and second will be in-person clinical visits and the other follow-ups could either be conducted in-person at the clinic or via teleconference - video:

a) Visit 1: in-person clinic visit

- At the first visit to the clinic, the physician or nurse will verify the patient's name and date of birth, and will collect information about pain, current and past medicines, and general health. The physician will perform a physical examination and measure heart rate, blood pressure and respiratory rate, and conduct a neurological exam.
- Baseline questionnaires will be taken, including Pain (NRS), Concussion Symptom Score, MIDAS/PedMIDAS, Anxiety, Depression, FDI, and QL.

At the end of the visit, all enrolled patients will be randomized to one of the two minimally invasive procedures, the ONB or the CMBB. Information from the patient's most recent clinical visit note (retrieved from the patient's medical record) may be used to obtain Visit 1 data.

b) Visit 2: Cervical and medial branch block procedures

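### The 30% dropout allowance is miscalculated: 63 enrolled leaves about 22 per group, not the 24 the plan says it needs

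*Combined protocol and SAP*

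**What the plan says.** The sample-size paragraph in section I (Data Analysis Plan and Sample Size) has three steps.

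- Target: "In order to detect a 30% difference between treatment groups", with α of 0.05 and a β written as 0.8.
- Requirement: "we will need a sample size of 24 subjects per group".
- Allowance for loss: "Taking into consideration a 30% dropout rate during the study, we estimate a sample size of 63 subjects in the trial".

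Section D.3 randomizes patients to one of two procedures (ONB or CMBB), so the requirement is 48 in total. It also sets the length of follow-up: "All patients will be followed for 12 months after enrollment".

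Section E gives the outcome that the size should serve: "The primary outcome is defined as change in pain" intensity on the 0 to 10 NRS, collected weekly and later every two weeks. Section I analyses it as a continuous change from baseline: "Assuming normality, T-Tests will be conducted to investigate the differences between the two randomized" groups, with a Wilcoxon rank sum test if the data are not normal. It adds a longitudinal analysis: "Repeated measure analysis will be used to compare the pain, functional and QL scores over time between groups".

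On missing data, section I says only that they will be accounted for at the coding stage. I found no replacement of dropouts, no imputation method and no other definition of dropout.

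**The concern.** A dropout rate is a fraction of the patients enrolled. To end with 48 after losing 30%, one divides 48 by 0.7. Adding 30% to 48 gives a smaller number, and 63 looks like the result of that. If so, the paragraph contradicts itself: it names a number of subjects it needs, a loss it expects, and an enrolment that does not deliver the first after the second. The stated power would then not hold at the end of follow-up.

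Two weaker points sit in the same paragraph. The β of 0.8 is evidently power of 0.80 (β of 0.20), a labelling slip that changes no design number. The 30% difference comes without a scale, SD, response rates, sidedness or time point, so a reader cannot confirm that 24 per group suits a t-test on NRS change. That makes the 24 unverifiable; it does not show it to be wrong.

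**Working it through.** **Inputs.** From section I: 24 per group, 30% dropout, 63 enrolled, α 0.05, power read as 0.80. From section D.3: two groups, 12 months of follow-up. Assumed because not stated: 1:1 allocation and, unless noted, a two-sided test.

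**Reproducing the plan's 63.**

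- Multiplying: 2 × 24 × (1 + 0.30) = 48 × 1.3 = 62.4, rounded up to **63**. This matches.
- Dividing: 48 / (1 − 0.30) = 48 / 0.7 = 68.57, rounded up to **69**. This does not match.
- Per arm: 24 × 1.3 = 31.2, so 32 per arm (64 in total); 24 / 0.7 = 34.3, so 35 per arm (70 in total).

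Of these, only multiplication of the total gives 63.

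**Checking forwards.**

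- 63 × 0.7 = 44.1 evaluable, about 22 per group, roughly 4 short of 48.
- Largest loss at which 63 still leaves 48: 1 − 48/63 = 23.8%.
- 69 × 0.7 = 48.3 and 70 × 0.7 = 49, so either meets the requirement.

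**Power.** For a two-sample t-test with n per group and standardized difference d, power comes from the noncentral t distribution with 2n − 2 degrees of freedom and noncentrality d√(n/2). The plan gives no d, so I solved for the value at which 24 per group has exactly 80% power: d = 0.826. Holding d there with 63 enrolled:

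| Loss | Evaluable | Per group | Power |
|---|---|---|---|
| 0% | 63.0 | 31.5 | 90% |
| 10% | 56.7 | 28.4 | 86% |
| 20% | 50.4 | 25.2 | 82% |
| 23.8% | 48.0 | 24.0 | 80% |
| 30% | 44.1 | 22.05 | 76% |

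At exactly 22 per group the power is 76.3%. The difference detectable with 80% power is then 0.865 SD, against 0.826 SD at 24. A one-sided test gives d = 0.729 at 24 per group and 76.8% power at 22.

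**Can the 24 be checked?** Only under assumptions that the plan does not state.

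- If the 30% means 30 percentage points of pain reduction, 24 per group holds for an SD up to 30 / 0.826 = 36.3 points, and 22 per group for an SD up to 30 / 0.865 = 34.7 points.
- If it means a 30-point difference in responder rates with a lower rate of 10% to 60%, the usual formulas for two proportions without continuity correction give 29 to 43 per group two-sided and 23 to 34 one-sided. Outside that range 24 can be enough: at a lower rate of 0% or 70% the two-sided requirement is about 18 to 21.

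**The case against.** The arithmetic is hard to dispute, so the case for the plan concerns how much it matters.

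**No primary time point is named.** The only efficacy decision in the documents is the four-week evaluation in section D.3, after which patients with less than 50% pain reduction may cross over. The 30% is loss over the whole study and need not apply at four weeks. If the powered comparison is early, 63 is adequate for any loss up to 23.8%. This stands as a limit on the consequence: the shortfall belongs to a 12-month comparison. It does not make the paragraph consistent, because the paragraph itself sets the 30% against the 24.

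**A repeated-measures analysis is planned.** Patients who leave could still contribute their earlier scores, which may recover some information. That is fair, but no model or missing-data assumption is given, and the requirement is stated as subjects per group for a two-group comparison.

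**The 76% is conditional.** The 0.826 SD is solved from 24, not taken from the plan. If 24 was rounded up from just above 23, the underlying effect could be as large as about 0.84 SD, and power at 22 per group about 78%. This also stands: 76% to 78% is the fair range, given that 24 per group was right.

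**The size is small.** It is two patients per group, two to four points of power and about 0.04 SD, with no bias in any estimate. The undefined effect size is arguably the larger weakness. I agree that the loss is modest. The enrolment figure is still wrong as written, and correcting it costs little.

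**Conclusion.** The concern holds. With 24 per group needed and 30% lost, 63 enrolled is the wrong figure: it supplies about 44 evaluable patients, 22 per group, where the matching enrolment is 69 (70 for equal arms). Nothing else in the documents closes the gap.

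The effect is modest. Power for a 12-month comparison is about 76%, not 80%, and earlier comparisons are less affected or not affected. This rests on 1:1 allocation, on reading the β as power of 0.80, and on accepting that 24 per group gives 80% power, which the plan does not let a reader confirm. The dropout error itself does not depend on how the 24 was obtained. It should be fixed.

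**What to change.** In section I, first state what the 30% difference refers to (scale and time point), the SD or response rates behind it, and whether the test is two-sided. Write power 0.80 (β 0.20) in place of a β of 0.8.

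Then correct the dropout step. If the test is two-sided and the comparison is at 12 months, wording such as this would serve:

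> Two-sided alpha 0.05, power 0.80 (beta 0.20). With 63 enrolled and 30% dropout, 44 patients (22 per group) are expected to be evaluable at 12 months. This detects a difference of 0.86 SD in NRS change with 80% power by t-test; power is about 76% for 0.83 SD, the difference that 24 per group detects with 80% power.

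If another time point is chosen, replace the 12 months and the 30% with that time point and the loss expected by then, and take the power from the table above.

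This costs wording only, with a slightly less favourable stated power or detectable difference. If the claim of 24 evaluable per group is to stay, the enrolment figure has to become 69, or 70 for equal arms, which is 6 to 7 more patients.

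### A normality check decides after the data are seen whether the primary pain (NRS) result compares means or ranks; this matters if the arms differ in distributional shape

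*Combined protocol and SAP*

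**What the plan says.** Section E (Primary Outcome Measures) sets the endpoint: "The primary outcome is defined as change in pain" intensity on the NRS, where "Patients will rate their pain score on a scale of 0 to 10". The scores are "collected at baseline, weekly for two months, and then bi-weekly throughout rest of the study". No single primary time point is named there.

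Section I (Data Analysis Plan and Sample Size) treats the NRS, MIDAS/PedMIDAS, FDI and QL scores as continuous and adds: "Differences of these parameters from baseline will be the outcomes variables". The choice of test then has two steps. First, "The differences in pain, functional, and QL scores will first be tested for normality". Second, "Assuming normality, T-Tests will be conducted to investigate the differences between the two randomized" groups, with this alternative: "If data does not appear to be normal, Wilcoxon Rank Sum Tests will be performed in contrast to T-Tests".

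Shapiro-Wilk is named in Section I for age and BMI, and for fluoroscopy time and radiation exposure, but not for the outcome scores. Section I also plans a repeated-measures comparison and a multiple regression. Neither depends on the normality check, and neither is designated primary.

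**The concern.** The two branches answer different questions. The t-test addresses the difference in mean change. The rank-sum test addresses whether a patient in one arm tends to have a better change than a patient in the other, and it yields no mean difference. The plan fixes no effect measure, so the form of the primary result, and of any confidence interval, is unknown until the data have been inspected. Each outcome could also land on a different branch.

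The gate leaves room for discretion as well. Without a named test, a threshold, a pooled or per-arm rule and a time point, two analysts could follow the text faithfully and report different primary analyses.

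At stake is the meaning of the primary comparison. If the arms differ in shape as well as, or instead of, location, the two branches can give different answers. A significant result from the rule then need not mean that mean pain change differs.

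**Working it through.** **Inputs.** From Section I: alpha 0.05, power 0.80 (the plan writes this as beta of 0.8), 24 per group, 63 in total. Not in the documents, and so assumed: the SD of NRS change (range 1.0 to 3.7), whole-number recording, Shapiro-Wilk at 0.05 as the normality test, and two-sided testing.

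**The plan's own figures.** The 24 per group cannot be derived from the stated inputs, because no SD or response rates are given. With n = 2(1.96 + 0.84)²/d², a standardised effect d = 0.81 gives 15.7/0.656 = 23.9, so 24. That would correspond, for example, to 3 NRS points with SD 3.7 (3/3.7 = 0.81). The total reproduces as 48 × 1.3 = 62.4, rounded up to 63. The checks below use 24 per arm and d = 0.81.

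**Step 1: the two targets.** Let Y be the change in NRS.
- t-test: Δ = E(Y in one arm) − E(Y in the other), null value 0.
- Rank-sum test: θ = P(Y₁ < Y₂) + ½P(Y₁ = Y₂), null value 0.5.

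If the arms differ only by a shift, Δ = 0 and θ = 0.5 hold together. If they differ in shape, Δ can be 0 while θ is not 0.5.

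**Step 2: same shape in both arms.** Latent changes were normal and recorded in whole points, 24 per arm. Rates at which the rule goes to the rank-sum test:

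| SD of change | Pooled check, rounded | Either arm fails, rounded |
|---|---|---|
| 2.0 | 34% | 30% |
| 2.5 | 19% | 23% |
| 3.0 | 13% | 17% |
| 3.7 | 9% | 14% |

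Without rounding, the rates are about 5% (pooled) and 9-10% (either arm). Rounding therefore moves the branch, strongly at small SDs and weakly at SD 3 or more. It hardly moves the conclusion. With baseline and follow-up rounded and clipped to 0-10 (assumed baseline mean 6.5, SD 1.8):
- Type I error, SD 1 to 3: always-t 0.048 to 0.051, two-step rule 0.048 to 0.052.
- Power at d = 0.81: always-t 0.73 to 0.75, always rank-sum 0.71 to 0.73, two-step rule 0.72 to 0.74.

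With rounded normal changes and the pooled check (SD 2 to 3), the two-step rule and always-t reached different decisions in 0.2-0.5% of null trials and 0.7-1.8% of trials at d = 0.81.

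**Step 3: equal means, different shapes.** One arm is homogeneous with mean μ. The other mixes a share p of large responders with non-responders so that p·μ_R + (1 − p)·μ_N = μ. Then Δ = 0 by construction.

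| Assumed case | Two-step rule rejects | t-test rejects |
|---|---|---|
| Mild, p = 35% | 7.4% | 5.4% |
| Mild, p = 25% | 8.4% | 5.5% |
| Mild, p = 20% | 8.4% | 5.6% |
| Mild, separate mixture, p = 20-35% | 6.9-8.1% | 4.7-5.2% |
| Stronger mixtures | 12-18% | about 6% |
| Strongest, p = 30%, μ = −1.5 | 21% | 6% |

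With 6,000 runs the Monte Carlo standard error near 5% is √(0.05 × 0.95/6000) = 0.0028, about 0.3 percentage points, so the excess is not simulation noise. In the strongest case the rank-sum branch was chosen in 99% of trials and θ was 0.59, not 0.5. The rank-sum test was therefore detecting a real difference in ranks. These rejections are errors only when read as a statement about means.

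**Step 4: heavy tails.** In two assumed same-shape cases with heavy-tailed changes, the two-step rule had more power than the t-test: 53% against 43% (t with 3 df, shift 1.6 points) and 76% against 63%.

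**Step 5: visit by visit.** The plan does not say whether the check is made once or at each visit. If it is repeated over 8 visits (pooled, whole-number scores, assumed correlation 0.6), both tests are used within one trial in 95%, 76% and 64% of trials at SD 2, 2.5 and 3.

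**The case against.** The strongest defence is that the rule is conventional, is written down in advance, and causes no material loss when the arms share a shape. Step 2 bears this out. The ungated repeated-measures and regression analyses would supply covariate adjustment and a mean-based comparison. The rank-sum fallback also protects power against heavy tails, as Step 4 shows. All of this stands, except that the ungated analyses do not cure the problem while neither is called primary.

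Three stronger readings are tempting and are not supported.

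- A reader might infer that rounding often decides the trial's result. The documents give no SD of change and do not state whole-number recording. Even granting both, rounding changes which test is used far more often than what is concluded.
- A reader might infer that a real treatment effect, with the arms pooled, would itself look non-normal. For two unrounded normal arms of 24, pooled Shapiro-Wilk rejected in 5.3% of trials at d = 0.5, 4.5% at 0.81, 4.0% at 1.0 and 1.5, and 5.0% at 2. It rose only at d = 2.5 (14%) and d = 3 (33%), far above the effect that 24 per group implies.
- A reader might infer that the two-step rule generally costs power. One assumed mixture (55% against 25% large responders) gave 43% against 48% for the t-test, but the heavy-tailed cases go the other way.

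**Conclusion.** The point holds as one about what is being compared. The plan lets an unspecified normality check decide, after the data are seen, whether the primary NRS comparison is of means or of ranks, and no effect measure is fixed.

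The size depends on shape. With a common shape the effect on error and power is negligible. With equal means and a responder subgroup in one arm only, the rule rejects in about 7-8% of trials in mild cases and 12-21% in stronger ones, where the t-test stays at 5-6%. These rates rest on assumed mixtures, on Shapiro-Wilk at 0.05 and on 24 analysed per arm. They show what could happen and do not predict this trial. Such a subgroup is plausible: the protocol itself splits patients at 50% pain reduction (Sections A and D.3), and its Aim 3 hypothesis ties response to examination findings and anatomic diagnosis. Nothing in the documents shows that the arms will differ in this way.

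A general claim of inflated type I error would go too far. The change is worth making because it gives the trial one prespecified estimate at almost no cost, not because the planned rule is invalid.

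**What to change.** In Section I, delete the normality gate for the primary NRS outcome and prespecify one analysis: the between-arm difference in mean change with its 95% CI, from a linear model that preferably adjusts for baseline NRS, at one time point named in advance by the trial team. The planned repeated-measures model could serve if it is designated primary and its contrast at that time point is specified. Keep the rank-sum test as a labelled sensitivity analysis, reported whatever the distribution looks like.

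Robust (HC3) or permutation p-values are optional. Whether to apply the same rule to skewed scores such as MIDAS is a matter of choice. Rounding was examined only for the NRS, and the FDI, scored 0 to 60, is much finer.

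The cost is a few sentences of analysis text, with no added patients or data and no change to the sample size. The one real downside is some loss of power in the primary test if NRS changes prove heavy-tailed. The sensitivity analysis would make that visible.

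### Baseline NRS is collected but is a named covariate in no planned analysis; adjusting the between-group comparison for it would usually gain precision at almost no cost

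*Combined protocol and SAP*

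**What the plan says.** Section E (Primary Outcome Measures) defines the primary outcome as change in pain "intensity scores (NRS), which will be collected at baseline, weekly for two months, and then bi-weekly throughout rest of the study". Section D.3 lists NRS among the Visit 1 baseline questionnaires, so the baseline value will exist for enrolled patients.

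Section I then states: "Differences of these parameters from baseline will be the outcomes variables". For the comparison between arms it says "Assuming normality, T-Tests will be conducted to investigate the differences between the two randomized" groups, and "If data does not appear to be normal, Wilcoxon Rank Sum Tests will be performed in contrast to T-Tests".

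Two further analyses follow in the same section:

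- "Repeated measure analysis will be used to compare the pain, functional and QL scores over time between groups and compared with baseline values". No model is written down.
- "We will also use multiple regression analysis where treatment, epidemiological, clinical, and psychosocial characteristics will be used as independent variables". The regression outcome is not named, and the covariates are given only as broad classes.

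No analysis is labelled primary, and no time point is named for the change score.

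**The concern.** Subtracting baseline from follow-up is an adjustment with the slope fixed at 1. When the true slope of follow-up on baseline differs from 1, the change score carries avoidable noise. ANCOVA estimates the slope from the data and removes that noise.

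The trial is small: 24 per group by the plan's own calculation, with 30% dropout allowed for. A wider interval than necessary therefore matters, and the information needed to narrow it is already being collected. At 22 to 24 per arm a chance imbalance in baseline pain is also plausible, and ANCOVA handles it with an estimated slope.

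This is a question of efficiency. The planned t-test is unbiased under randomisation, and no type I error or power harm is claimed for the normality pre-test. The pre-test only leaves open whether a mean difference or a rank comparison will be reported.

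**Working it through.** **Inputs from Section I.** Alpha 0.05 (taken as two-sided), 80% power (printed as a beta of 0.8), 24 per group, 30% dropout, 63 in total.

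**The plan's own figures.** The total follows from 48 × 1.3 = 62.4, rounded up to 63. The 24 per group cannot be reproduced directly, because the 30% difference comes with no SD and no response rates. If it is read as 80% power for a two-sided t-test, the noncentral t distribution gives a standardised effect of d = 0.826 SDs of change. That value is back-solved and is not stated in the plan. Applying the whole-study dropout, 63 × 0.7 / 2 = 22 completers per arm, where the same t-test has 76.3% power.

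**Assumed inputs.** ρ is the correlation between baseline and follow-up NRS; k is follow-up SD divided by baseline SD. The documents give neither, so ranges are shown.

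**Variance ratio.** Per patient, with baseline variance set to 1:

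- change score: 1 + k² − 2ρk
- ANCOVA residual: k²(1 − ρ²)
- ratio: R = k²(1 − ρ²) / (1 + k² − 2ρk)

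The denominator minus the numerator is (1 − kρ)², which is never negative. So R never exceeds 1, and it equals 1 only when kρ = 1. With k = 1, R reduces to (1 + ρ)/2.

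**Finite-sample cost.** Estimating the slope multiplies the variance by 1 + 1/(2n − 4) and leaves 2n − 3 error degrees of freedom instead of 2n − 2. ANCOVA power is therefore taken from the noncentral t with effect d / √(R·(1 + 1/(2n − 4))) and 2n − 3 df.

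**Confidence interval width at 22 per arm, k = 1.** This needs no assumed effect. For ρ = 0.5, √(0.75 × 1.025) = 0.877; the change from 42 to 41 df makes almost no difference. For ρ = 0.3, 0.5, 0.7 and 0.9 the widths are 0.82, 0.88, 0.93 and 0.99 of the planned width.

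**Power of ANCOVA (R in brackets).** The unadjusted t-test has 80% at 24 per arm and 76.3% at 22.

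| n per arm | k | ρ = 0.3 | ρ = 0.5 | ρ = 0.7 | ρ = 0.9 |
|---|---|---|---|---|---|
| 24 | 1.0 | 93.0% (0.65) | 89.2% (0.75) | 85.2% (0.85) | 81.1% (0.95) |
| 22 | 1.0 | 90.6% (0.65) | 86.2% (0.75) | 81.8% (0.85) | 77.4% (0.95) |
| 22 | 1.2 | 85.7% (0.762) | 80.8% (0.871) | 76.7% (0.966) | 76.2% (0.977) |
| 22 | 1.4 | 82.1% (0.841) | 77.7% (0.942) | 75.3% (1.000) | 81.9% (0.846) |

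Ten of the twelve cells at 22 per arm gain. The largest loss is 76.3% to 75.3%. Because R cannot exceed 1, that is the limit for any ρ and k at this sample size.

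**Simulation check.** With 40,000 trials per cell at 22 per arm and k = 1, ANCOVA power was 90.8, 86.0, 81.6 and 77.1%, against 75.9 to 76.4% for the change-score t-test. Type I error of both tests was 0.048 to 0.052 in every cell at 22 and 24 per arm.

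**The case against.** A t-test on change is a standard, interpretable analysis of the outcome as Section E defines it, so this is a preference about efficiency and not an error. That is correct, and it limits how strongly the point can be put.

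The gain may be small. The protocol splits response at 50% pain reduction, and a mixture of responders and non-responders spreads follow-up scores, so k may exceed 1. A simulation of a bounded integer NRS with such a mixture (baseline about 6.5, SD 1.6, several assumed pairs of responder rates, 22 per arm) gave k of 1.3 to 1.6, ρ of 0.43 to 0.65, and power gains of only 0 to 3 points. This stands as a caution against relying on the k = 1 row. Even so, no scenario in that simulation showed a loss.

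The 22 per arm uses 12-month dropout, while a week-4 analysis would lose fewer patients. At 31 per arm, with the same d, the t-test already has 89.3% power. ANCOVA gives 95.6% (ρ = 0.5) or 93.1% (ρ = 0.7) at k = 1, and 90.4% or 88.7% at k = 1.4. Precision is then less strained, but ANCOVA still wins or comes within about 0.6 points.

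The other planned analyses might already adjust. Clinical characteristics in the regression could include baseline pain, and a repeated measures model with a common baseline mean would recover much of the gain. Neither is specified, and neither analysis is labelled primary. The gain shown is against the t-test only; the Wilcoxon branch was not quantified.

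MIDAS/PedMIDAS and QL/PedsQL pair adult and paediatric instruments, so one slope across both is an approximation. Under randomisation it introduces no material bias.

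**Conclusion.** The point holds. The first-listed test of the primary outcome ignores a covariate already in hand, and no other analysis in the plan names it. The planned test remains valid.

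The loss is one of precision. At 22 per arm and k = 1, adjustment removes about 1% to 18% of the confidence interval width for ρ from 0.9 down to 0.3. The corresponding power gain is about 1 to 14 points if d = 0.826. At k = 1.2 or 1.4 the result ranges from a loss of about 1 point to a gain of about 9. The width ratios rest on ρ and k; the power figures also rest on the back-solved effect. The change should be made because the possible gain is much larger than the possible loss, not because any one gain is assured.

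**What to change.** In Section I, prespecify one primary analysis: an ANCOVA of NRS at a named time point on treatment, with baseline NRS as covariate, reporting the adjusted mean difference with its 95% confidence interval.

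I suggest week 4. Section D.3 assesses "pain reduction on receiving the block evaluated after four weeks", and cross-over becomes possible after that. The SAP must also say whether week 4 is counted from the block or from enrolment, since Section D.3 assesses response after the block but times the follow-up visits from enrolment.

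An equal alternative is to write out the repeated measures model with baseline NRS, week, treatment and treatment-by-week, and name the week-4 contrast as primary.

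Keep the Wilcoxon test as a named sensitivity analysis in place of the switch on normality.

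Use the same baseline adjustment for FDI, QL and MIDAS/PedMIDAS, with a time point named for each. Table 1 first repeats Quality of Life at 2 months and Migraine disability at 3 months, so week 4 cannot serve those two under that schedule.

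The cost is SAP wording and about one degree of freedom (46 to 45 at 24 per group). It needs no extra patients, visits or data.
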